# 4.7.3 Premature Termination or Suspension of Study

This study may be temporarily suspended or prematurely terminated if there is sufficient reasonable cause. Written notification, documenting the reason for study suspension or termination, will be provided by the suspending or terminating party to the NIH. If the study is prematurely terminated or suspended, the PI will promptly inform the IRB and will provide the reason(s) for the termination or suspension. Circumstances that may warrant termination or suspension include, but are not limited to:

- Determination of unexpected, significant, or unacceptable risk to participants
- Demonstration of efficacy that would warrant stopping
- Insufficient compliance to protocol requirements
- Data that are not sufficiently complete and/or evaluable
- Determination of futility

Study may resume once concerns about safety, protocol compliance, and data quality are addressed and satisfy the sponsor and/or IRB.

# 5 Behavioral/Social Intervention

# 5.1 Study Behavioral or Social Intervention(s) Description

We propose to combine moderate intensity aerobic exercise with lower-extremity specific resistance training, which is expected to reverse DPN symptoms. While current ADA (Americans with Disabilities Act) and American College of Sports Medicine (ACSM) guidelines emphasize the benefits of combination (i.e., aerobic and resistance) training programs, there is significant heterogeneity in the duration, intensity, frequency and specific exercises used in resistance training programs. Since DPN is length-dependent, distal extremities are more severely affected [57]. While most previous studies have assessed thigh skeletal muscle, we will assess the plantar flexors. Previous studies have demonstrated that significant impairments exist in lower extremity muscles in individuals with DPN, most notably lower plantar flexor strength and flexibility [58, 59]. Therefore, we expect an exercise intervention that combines aerobic training and strength training of the lower extremity will further reverse DPN symptoms.

## 5.1.1 Administration of Intervention

The exercise intervention will be administered in person at NYU's Department of Physical Therapy, [name]. The site PI ([name]) and Research Associate will supervise all procedures. Health professional students may assist [name] and the Research Associate. The 10-week intervention has been previously published [24] and will include 3 days a week of moderate intensity aerobic and resistance training. Each session will last 60-90 minutes.

## 5.1.2 **Procedures for Training Interventionalists and Monitoring Intervention Fidelity**

The exercise intervention will be administered by licensed physical therapists or health professionals with exercise training. Each participant will follow a previously published 10-week moderate intensity aerobic and resistance exercise program [24]. Participants will be allowed to choose their modality (treadmill or recumbent stepper). At each session, modality, repetitions, heart rate, and rate of perceived exertion (RPE) will be recorded. Fidelity will be monitored by tracking the duration, intensity, and frequency of exercise. Additionally, for resistance training, weights and repetitions will be assessed.

The following criteria will be used to signal inadequate fidelity:

- 1. Aerobic training:
- a) Does not complete duration
- b) Does not reach prescribed intensity
- c) Does not complete prescribed frequency (days per week)
- 2. Resistance training:
- a) Does not complete all exercises
- b) Does not complete prescribed number of repetitions
- c) Does not reach prescribed intensity (i.e., uses lower or higher resistance)
- d) Does not complete prescribed frequency (days per week)

At each session, interventionists will verbally encourage subjects to reach exercise prescription goals. Failure to maintain frequency, duration, or intensity will be documented.

Quarterly review with the research team with be instituted to review intervention fidelity and deploy remedial strategies for interventionists.

# 6 Study Procedures and Schedule

# 6.1 Schedule of Events

See Attachment A 'Schedule of Events'.

## 6.1.1 Standard of Care Study Procedures

N/A

# 6.2 Laboratory Procedures/Evaluations

## 6.2.1 Clinical Laboratory Evaluations

All subjects will undergo a 5-sample (10x4 mL of blood) oral glucose tolerance test (OGTT) at NYU CBI, where we carry out all evaluations involving intravenous (IV) catheters. We will ask subjects to abstain from taking oral medications such as metformin for 2 full days prior to all OGTT evaluations in order to obtain results that are unbiased by medication effects, which typically trigger insulin release from the pancreas or reduce glucose production in the liver. The rationale for doing the pre and post-intervention OGTT is to measure the degree of insulin resistance. Exercise has been shown to improve insulin sensitivity in patients with diabetes. We want to see if improvement in insulin sensitivity is correlated with MRI metrics. The OGTT has been used as a safe and standard procedure in our laboratory, and has been approved by our IRB for several years (s15-00271). We will document all those medications and changes and if needed, will account for them statistically. Subjects will be asked to abstain from taking their insulin on the morning of their visit. All diabetes medications will be brought to the visit so that they may be taken at the conclusion of the evaluation for which they need to be fasting for, and around the time they are given food prior to completion of the visit. Studies are performed in the morning after an overnight fast. Baseline bloods are obtained at time 0, prior to the consumption of the 75g glucose drink. We also obtain blood samples to measure inflammation that will help account for variable physiological

#### CONFIDENTIAL

conditions such as time of day and other risk factors. For the OGTT, samples are then collected at 30, 60, 90, and 120 minutes post glucose ingestion. We will compute the Matsuda whole body Index of Insulin Sensitivity (ISI) as follows and will be used at the insulin resistance (IR) variable:

 $ISI = \frac{10,000}{\sqrt{[fasting glucose x fasting insulin] x [mean glucose x mean insulin during OGTT]}}$ 

Baseline bloods obtained at time 0 will also be analyzed for measuring HgbA1C and C-reactive protein (CRP). In addition, we will use baseline bloods to estimate levels of hydrogen peroxide as a marker of ROS. None of these blood biomarkers will be used as an inclusion/exclusion criterion.

# 6.3 Imaging Procedures

All experiments will be performed on a 3T whole body scanner (Magnetom Prisma; Siemens Medical Solutions, Germany) available in the Department of Radiology at the NYU School of Medicine. We will use our recently developed dual-tuned (31P/1 H) coil array (C.1.6). The MRI scan will include 31P-MRI measurement of muscle oxidative capacity following a 90-second plantar flexion exercise at 40% MVC (Section C.1.1,2), dynamic post-contractile BOLD-measurements following brief 100% MVC every 90 s (Section C.1.3), IDEAL MRI for IMAT calculation, and DTI for assessment of peripheral nerve integrity (FA and ADC). The main MRI sequences and their acquisition parameters are summarized in Table 1. Additional sequences will include localizers and anatomical images for segmentation purposes.

#### Table 1: MRI Sequences and Imaging Outcomes

Pulse Sequence Description	TA (mm:ss)	N	TTA (mm:ss)	Exercise/Resting	Outcomes
PCr Mapping with  P-FLORET	1:00	5	05:00	Resting	Resting [PCr]
PCr Resynthesis with  P-FLORET	0:06	72	7:30	2-min plantar flexion at 40% MVC	PCr Resynthesis Rate
IDEAL-MRI	5:00	1	5:0 0	Resting	Water Fat Fractions
BOLD-MRI	0:01	600	10:00	1-rep at 100% MVC every 90s	∆ 1 2*; TTP
DTI	3:08	2	6:15	Resting	FA, ADC

N: number of acquisition/averages; TA: acquisition time for one average. FA: fractional anisotropy. ADC: apparent diffusion coefficient TTA: Total time of acquisition for experiment: TTP: Time-to-Peak

# 6.4 Study Schedule

### 6.4.1 Baseline Visit

### 6.4.1.1 Step 1: Consent

The PI, Co-Investigator, Research Coordinator, or Research Data Associate will consent individuals at the Center for Biomedical Imaging. They will go over the consent form with the subject and answer any questions that may arise. When the subject has shown that he/she understands the process and has signed the form, he/she will be given a copy of the form and considered "enrolled" in the study.

All subjects will have the option to consent remotely (through send safe) instead of consenting in person. If the subject prefers to sign the consent form electronically, the research coordinator will be able to send the informed consent via email (send safe) to the subject. The research coordinator will go over the consent form with the subject and will give ample time to the subject to ask questions regarding the study,

### 6.4.1.2 Step 2: Blood draw

After the consent process is completed, participants will be required to have blood tests at the CBI or at the outpatient lab located at TISCH hospital. At CBI a licensed nurse, radiology technician, or study team member with phlebotomy certification will place the IV line and at the outpatient lab at Tisch hospital a

#### CONFIDENTIAL

This material is the property of the NYU School of Medicine and Langone Medical Center. Do not disclose or use except as authorized in writing by the study sponsor

nurse will be performing the blood draw. A total of 14 tubes, approximately 59.2 mL of blood, will be collected. The following blood tests will be performed:

- Insulin (fasted) •
- Glucose (fasted)
- Complete Blood Count with Differential •
- **Comprehensive Metabolic Panel** •
- Lipid profile •
- Fibrinogen •
- Highly sensitive CRP
- **Thyroid Stimulating Hormone** •
- Hemoglobin A1C •
- OGTT: subject will drink a sweet-tasting drink and then have his/her blood drawn (2 tubes) every 30 minutes for a 2-hour duration.

The following urine test will be performed:

Microalbumin

Note: The Center of Biomedical Imaging as well as other NYU Health Institutions are taking safety measure necessary to reduce the risk of subjects contacting COVID-19. As per NYU COVID-19 related policies, staff will ensure all rooms or MRI machines are disinfected prior to the subjects scan.

### 6.4.1.3 Step 3: MRI Session

The MRIs will be performed on the day of consenting and blood tests, also at the CBI on the FDAapproved 3T whole body scanner.

All MRIs are reviewed by the licensed clinical radiologist on duty immediately as they are done. A report is issued and faxed to the PI the same day with the radiologist's interpretation of the scan as well as recommendations based on any incidental findings. In the case of an incidental finding, either the PI or another investigator on the study will speak to the subject in person at their next visit or via phone regarding the new information. Types of incidental findings would be a bone infarct, meniscal tear, or meniscal destruction found on the MRI. A copy of the original image report will also be provided to the patient in person and they will be encouraged to follow up on the discovery with their treating physician. We will ask subjects to abstain for 2 full days prior to their MRI scan from taking oral diabetes medications such as metformin. Subjects will be asked to fast the night prior to visit. Subjects will be asked to not take their insulin on the morning of their visit. All diabetes medications will be brought to the visit so that they may be taken at the conclusion of the evaluation for which they need to be fasting for.

## 6.4.2 Maximal Graded Exercise Testing (VO2R Assessment)

Maximal graded exercise testing (VO2R assessment) will be performed prior to the 10-week exercise intervention by an exercise physiologist at Langone Orthopedic Center, [name]. A standardized exercise protocol with a recumbent stepper/treadmill will be used (Trackmaster, USA). We will use a ramping protocol with increases in workload equivalent to 0.5 METS per 1 minute. Continuous monitoring of heart rate will be performed. Additionally, blood pressure and RPE are measured at the end of each stage. Criteria for a "maximal" effort during exercise testing include: reaching a plateau in VO2 with increased workload, a respiratory exchange ratio of greater than or equal to 1.15, a peak HR within 85% of the age-predicted maximal HR (in absence of beta blockage), and an RPE of greater than or equal to 18 (ACSM Guidelines for Exercise Testing and Prescription 10th edition, 2017.) The test will be stopped before maximal effort was achieved if any of the following occur: angina, dyspnea, fatigue (voluntary exhaustion or inability to maintain a speed/cadency of 115 on the stepper), hypertension (250 mm Hg systolic or 115 mm Hg diastolic), and hypotension (>10mmHg drop in blood pressure with workload increase), or ischemic electrocardiographic abnormalities. The same exercise physiologist will administer tests (before and after intervention). In addition to standardized protocols, the following procedures will be used to minimize bias: 1) The use of timed encouragement scripts

2) No review of pre-intervention test results before post intervention tests

CONFIDENTIAL

This material is the property of the NYU School of Medicine and Langone Medical Center. Do not disclose or use except as authorized in writing by the study sponsor

All procedures related to exercise intervention and its safety have been previously published in the peerreviewed literature [15, 24, 60-62]. Each participant will be prescribed an individualized, 10-week exercise program (after the 4-week non-exercise phase) with both aerobic and resistance components, based on the ACSM Guidelines [15, 24]. Exercise training will be performed under the supervision of a licensed physical therapist at the Department of Physical Therapy, [name]. Participants will have the choice of using a treadmill or a recumbent stepper. The physical therapist will monitor blood glucose level, blood pressure, heart rate, and RPE during each exercise session.

Additionally, in light of the COVID-19 pandemic, all subjects will be required to complete the PCR Covid test at a site that is convenient for them.

Note: Due to COVID-19 one of the requirement policy for the Department of Physical Therapy is to complete the PCR test within 5 days prior to patient's appointment. It is required that all subjects complete this testing as a way to reduce the risk of patients contacting COVID-19.

**Aerobic Exercise:** The maximal workload obtained from the VO2R assessment will be used to calculate a moderate level of intensity (50–70% of VO2 reserve) for the aerobic training program. A brief overview of the program is provided in Table 2.

Table 2

Week	Day 1	Aerobic Exercise	Resistance Exercise
1	1	30 mins, 50% VO 2 R	Determine 1 RM max, 10 reps x 1 day,
			Record medication use, Utah Early Neuropathy
			Scale, Give Actigraph
	2	30 mins, 50% VO 2 R	PROMIS Physical Function and Fatigue,
			Calf muscle performance
	3	35 mins, 50% VO 2 R	9 item Physical Performance Test
2	1	35 mins, 50% VO 2 R	Get Actigraph, 10 reps
	2	35 mins, 50% VO 2 R	15 reps
	3	40 mins, 50% VO 2 R	
3	1	40 mins, 50% VO 2 R	15 reps
	2	40 mins, 50% VO 2 R	15 reps
	3	45 mins, 50% VO 2 R	
4	1	45 mins, 50% VO 2 R	15 reps
	2	45 mins, 50% VO 2 R	15 reps
	3	45 mins, 50% VO 2 R	
5	1	45 mins, 60% VO 2 R	15 reps
	2	45 mins, 60% VO 2 R	15 reps
	3	45 mins, 60% VO 2 R	
6	1	45 mins, 70% VO 2 R	15 reps
	2	45 mins, 70% VO 2 R	15 reps
	3	45 mins, 70% VO 2 R	
7	1	50 mins, 70% VO 2 R	20 reps
	2	50 mins, 70% VO 2 R	20 reps
	3	50 mins, 70% VO 2 R	
8	1	50 mins, 70% VO 2 R	20 reps
	2	50 mins, 70% VO 2 R	20 reps
	3	50 mins, 70% VO 2 R	
9	1	50 mins, 70% VO 2 R	20 reps
	2	50 mins, 70% VO 2 R	20 reps

CONFIDENTIAL

This material is the property of the NYU School of Medicine and Langone Medical Center. Do not disclose or use except as authorized in writing by the study sponsor

	3	50 mins, 70% VO 2 R	Give Actigraph
10	1	50 mins, 70% VO 2 R	20 reps
	2	50 mins, 70% VO₂R	PROMIS Physical Function and Fatigue,
			Calf muscle performance
	3	50 mins, 70% VO 2 R	9 item Physical Performance Tests,
			Get Actigraph

**Resistance Training:** will include the following exercises: biceps/triceps curls, seated row, squats, and heel raises. Dumbbells will be used for strength training, with resistance levels gradually increased to maintain RPE in a moderate range (7–8 out of 10) for each participant. The weight of the dumbbells will be based on RPE 5-7, on a scale of 0-10, and 50-70% of 1 repetition maximum weight. There will be 1 to 5 minutes of rest between each exercise. We will use the following sequence of exercises in this study: Blood pressure, blood sugar check, warm-up, aerobic exercise, resistance exercise, and stretch.

Prior to each exercise session, the following will be assessed, consistent with guidelines set forth by the American Physical Therapy Association and American Diabetes Association.

- Foot: a visual inspection for cuts, blisters, cracked skin, and/or ulcer development
- Finger stick blood glucose:
  - If hypoglycemic (less than 100 mg/dL), carbohydrate snacks will be provided, and glucose testing will be repeated in 15-20 min.
  - If hyperglycemic (more than 300 mg/dL) and the participant was not taking insulin, exercise will be permitted with close monitoring of blood glucose every 10 to 15 minutes to ensure that the blood glucose level does not increase with activity.
  - If hyperglycemic (more than 300 mg/dL) and the participant was taking insulin, urine will be checked for ketosis. If the ketone test result is positive, then exercise will be postponed. If the ketone test result was negative, then exercise will be permitted with close monitoring of blood glucose every 10 to 15 minutes.
- Blood pressure: participants will not be permitted to exercise if blood pressure is higher than 200/110 mm Hg
- RPE will be assessed at baseline and every 20 minutes. A moderate RPE level (11–13 on the 17point scale) should be achieved at each session.

Adverse event tracking: Adverse events will be tracked at each session. Events will be classified as related to exercise intervention or unrelated to exercise intervention. Severity will be classified using the Common Terminology Criteria for Adverse Events (CTCAE) v5.0. [name]. will serve as the safety monitor for this study and review adverse events as necessary.

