# 2 Objectives and Purpose

# 2.1 Primary Objective

The primary objective is to assess and compare the interventions (exercise versus control phase) in terms of the baseline to follow-up change in the following outcomes: 1) DTI, plasma ROS level, and the MNSI assessment of DPN symptoms (Aim 1); and 2) leg mitochondrial function, oxidative capacity (31P-MRI), peak MV response (BOLD-MRI), the proportion of fat-free muscle (IDEAL-MRI) and leg muscle strength (Aim 2).

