# 3.2 Study Endpoints

# 3.2.1 Primary Study Endpoints

Body mass index (BMI), glycosylated hemoglobin (HbA1c), and C-reactive protein will be assessed before and after the 10-week intervention, along with the following measures of neuropathic symptoms: 1) MNSI symptom questionnaire with yes/no responses to 15 items indicating the frequency and severity of neuropathic symptoms and Patient-Reported Outcomes Measurement Information System (PROMIS) Physical Function and Fatigue subscales, which are computer adaptive tools, will be used to assess symptoms related to physical disability and fatigue [52]; 2) MNSI physical exam score, to indicate abnormalities in the appearance of the feet, vibration sense, reflexes, and monofilament sensation; 3) Vibration Perception Threshold (VPT) will be assessed on the plantar aspect of the great toe [53] and Calf Muscle performance will be quantified as peak ankle plantarflexion torque at 60 degrees/sec [54]; 5) Plasma levels hydrogen peroxide as marker of ROS; 6) Lower leg muscle performance will also be assessed using the 9-item Physical Performance Test [54]; and 7) the Utah Early Neuropathy Scale, which is a physical exam specific to early sensory predominant polyneuropathy. Physical activity will be quantified using a wearable activity monitor (actigraph) [55]. Subjects will be required to wear the actigraph for at least a week.

The following outcomes will be assessed through multinuclear-MRI: 1) PCr resynthesis rate in the gastrocnemius (G) and the soleus (S) muscle groups, following a 90-s plantar flexion exercise during which resistance is applied at approximately 40% of the individual's maximum voluntary contraction (MVC); 2) Time-to-peak (TTP) of the BOLD signal in the G and S muscle groups; 3) Peak  $\Delta T2^*$  at 100% isometric MVC in the G and S muscle groups; 4) IMAT in the G and S muscle groups using IDEAL MRI; 5) Fractional anisotropy (FA) in the tibial nerve using DTI; 6) Apparent diffusion coefficient (ADC) in the tibial nerve using DTI.

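### PROMIS, calf torque and the Physical Performance Test are first taken after training has begun, calf torque has no control-phase value, and the Utah scale has no follow-up

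*Combined protocol and SAP*

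**What the plan says.** Section 3.2.1 (Primary Study Endpoints) states that BMI, HbA1c and C-reactive protein "will be assessed before and after the 10-week intervention, along with the following measures of neuropathic symptoms". The list that follows includes the PROMIS subscales, calf performance, the 9-item Physical Performance Test and the Utah Early Neuropathy Scale. Strength is defined there: "Calf Muscle performance will be quantified as peak ankle plantarflexion torque at 60 degrees/sec".

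Section 2.1 sets the primary objective as to "assess and compare the interventions (exercise versus control phase) in terms of the baseline to follow-up change", and its Aim 2 list ends with "the proportion of fat-free muscle (IDEAL-MRI) and leg muscle strength (Aim 2"). Section 9.1 repeats this.

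The intervention is "3 days a week of moderate intensity aerobic and resistance training" (section 5.1.1) for 10 weeks. Table 2 in section 6.4 places the assessments inside it:

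- **Week 1, day 1:** "Determine 1 RM max, 10 reps x 1 day", plus the Utah scale.
- **Week 1, day 2:** "PROMIS Physical Function and Fatigue" and calf performance.
- **Week 1, day 3:** the Physical Performance Test.
- **Week 10, days 2 and 3:** the same tests again, without the Utah scale.

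Aerobic exercise is prescribed on every one of these days. On session order, the Resistance Training paragraph says: "We will use the following sequence of exercises in this study: Blood pressure, blood sugar check, warm-up, aerobic exercise, resistance exercise, and stretch". It does not say where the tests fall.

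Section 6.4.4 lists only blood tests, the VO2R test and MRI for the post-exercise visit. Attachment A marks PROMIS and calf performance in Weeks 7 and 16 only, and the Physical Performance Test in every week from 7 to 16. It has no row for the Utah scale.

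**The concern.** A change score for these measures is meant to describe what 10 weeks of exercise did. Under Table 2 the first value comes after the participant has begun training, has done a 1-RM determination and has worked through a resistance set that includes squats and heel raises. Soreness could lower the first calf torque or performance score. Familiarity with the tasks could raise it. The last value is taken while training continues, at a higher prescribed aerobic dose. If the tests follow the day's exercise, the two occasions also differ in what immediately precedes them.

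Two further gaps cannot be repaired in analysis. Calf torque has no value before Week 7, so it has no control-phase change to set against the exercise-phase change. The Utah scale has a first value and no second.

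**Working it through.** **The plan's own figure.** Section 9.4 gives a detectable within-subject change of 10% to 18% of the baseline mean (N = 40, 80% power, two-sided 5%). With (1.960 + 0.842) × SD of change / √40 and the exercise columns of Tables 3 and 4:

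- BOLD: 2.802 × 1.26 / 6.325 = 0.558; 0.558 / 3.24 = 17.2%
- PCr: 2.802 × 12.85 / 6.325 = 5.69; 5.69 / 41.16 = 13.8%
- MNSI: 2.802 × 1.78 / 6.325 = 0.788; 0.788 / 5.2 = 15.2%

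All three lie in the stated range. The calculation covers only these outcomes, so nothing below changes the sample size.

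**Session count.** Table 2 has 10 weeks × 3 days = 30 sessions. Session number = 3 × (week − 1) + day.

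| Measure | First test | Last test | Sessions done before first | Sessions done before last | Sessions covered |
|---|---|---|---|---|---|
| PROMIS, calf torque | 2 | 29 | 1 | 28 | 27 of 30 (90%) |
| Physical Performance Test | 3 | 30 | 2 | 29 | 27 of 30 (90%) |

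**Share of the aerobic dose covered.** Take minutes × fraction of VO2R as a rough index. The weekly sums are 47.5, 55, 62.5, 67.5, 81 and 94.5, then 105 in each of weeks 7 to 10, for a total of 828.

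- PROMIS and calf, tests before that day's exercise: (828 − 15 − 35 − 35) / 828 = 90%
- PROMIS and calf, tests after it: (828 − 15 − 15 − 35) / 828 = 92%
- Physical Performance Test, before: (828 − 15 − 15 − 35) / 828 = 92%
- Physical Performance Test, after: (828 − 15 − 15 − 17.5) / 828 = 94%

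**Dose around each test.**

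- Same day, PROMIS and calf: 30 × 0.50 = 15 at the first test and 50 × 0.70 = 35 at the last, a ratio of 2.33. This matters only if the tests follow the aerobic work.
- Same day, Physical Performance Test: 35 × 0.50 = 17.5 against 50 × 0.70 = 35, a ratio of 2.0, on the same condition.
- Preceding session, all three measures: 15 against 35, whatever the order within the day.

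**Control-phase strength.** Attachment A shows no calf test in Weeks 0 to 6. Section 4.7.2 refers to a post-non-exercise visit, but the body of section 6.4 gives no content for it. The control-phase change needs two values and the schedule provides none.

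**Utah scale.** Table 2 gives it once, on week 1 day 1. It is absent from week 10, from section 6.4.4, from the withdrawal visit in 6.4.5 and from Attachment A.

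**Physical Performance Test frequency.** Table 2 has two occasions. Attachment A marks ten weeks (7 to 16). Attachment A has week columns only, so it cannot settle the day or the order.

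**The case against.** The strongest reply is that little of the training contrast is lost, and that is right: 27 of 30 sessions lie between the two tests. A reader might infer that no improvement in these measures could be attributed to the programme at all. The documents do not support that. They give neither the size nor the direction of any soreness or practice effect.

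A reader might also infer that the follow-up is certainly taken under heavier fatigue. That is not supported either. The quoted sequence orders exercises, not assessments. The resistance column of Table 2 also holds items such as recording medication and handing out the activity monitor, so a test's place in it does not show that the test follows aerobic work. Minutes × %VO2R is an index made for this check, and the protocol sets the same moderate perceived-exertion target at each session. What stands is that the order is unspecified, and that the preceding sessions differ in prescribed dose in any case.

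On strength, section 9.2 has no strength hypothesis and section 9.4 no power statement for it. The MRI load is set from each participant's maximum voluntary contraction (MVC), so a plantar-flexion force may exist in the control phase. Both points are fair. But sections 2.1 and 9.1 name strength in the primary comparison, and the listed outcome is calf torque, not that force.

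Torque testing at an MRI visit has its own problem. It would put maximal plantar flexion close to PCr and BOLD measurements in the same muscles, at a fasted visit with diabetes medication withheld.

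**Conclusion.** The point holds as a conflict between the endpoint definition and the schedule, with three consequences of different weight.

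1. The strength comparison with the control phase is not computable from the listed outcome, and the Utah scale has no change score. Both follow directly from the schedule and need no assumption.
2. The first PROMIS, calf and Physical Performance Test values are not pre-intervention values as section 3.2.1 defines them. The loss of training contrast is small (3 of 30 sessions). The exposure to soreness and practice effects is real but cannot be quantified.
3. The 2.0- to 2.33-fold difference in same-day aerobic dose is conditional on the tests following that day's aerobic work, which the documents do not state.

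The disagreement between Table 2 and Attachment A on how often the Physical Performance Test is done is a separate inconsistency, to be settled at the same time.

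**What to change.** - **First battery.** Take PROMIS, calf torque, the Physical Performance Test and the Utah scale on exercise-week-1 day 1, before warm-up and before the 1-RM test. The alternative is the existing Week 6 visit, before the VO2R test.
- **Follow-up battery.** Take the same tests before any exercise that day, under the same conditions and in the same order, and include the Utah scale. With a day 1 baseline and the present follow-up days, the change would cover 28 of 30 sessions (PROMIS, calf) or 29 of 30 (Physical Performance Test).
- **Strength against control.** Either record and analyse the plantar-flexion MVC used to set the MRI load at Weeks 1, 5 and 18, or restate strength in 2.1 and 9.1 as an exercise-phase pre-post outcome only. The first option assumes that the MVC is measured at every scan and that all three scans take place: 1.2, 3.1 and Attachment A say three, while 9.3.1 says two. Calf torque testing should not be placed ahead of the MRI on the same day.
- **Text.** Reconcile 3.2.1, Table 2, 6.4.4 and Attachment A, including the number of Physical Performance Tests. State the test order within a session.
- **Participants already tested.** Record the session number and whether each test preceded exercise, and describe the result as a change from early to late training.

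The cost is a longer first exercise session (sessions are planned at 60 to 90 minutes) and a short added follow-up assessment. Testing ahead of the 1-RM could affect the 1-RM itself. The Week 6 option avoids that, but it puts the battery ahead of the VO2R test and needs the torque equipment at that site, which the documents do not address.
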